9. BIOLOGICAL SAMPLE

9.1. Biological samples

Biological material will be collected for:

(i) the standard analysis for determining inclusion / exclusion criteria:

- Blood sample testing
- Urinalysis and pregnancy test (if applicable).

(ii) the phenotypic assessment of the donors (baseline)

- Blood sample for serology and immunology assessments

(ii) the evaluation of the trial objectives:

- Blood, stools, nasal swabs and skin biopsies

After collecting samples, these will be labeled with the subject's identification number.

9.2. Standard laboratory analysis

9.2.1. Blood sample analysis

20mL of blood sample will be collected at enrolment visit (V0) for determining inclusion/exclusion criterion and 8mL at the last study visit (V2) and analyzed at local center.

Hematology/Hemostasis

Hematology assessments will include red blood cell count (RBC), hemoglobin (Hgb), hematocrit (Hct), mean corpuscular volume (MCV), white blood cell count (WBC) including differential (neutrophils, lymphocytes, monocytes, eosinophils, and basophils) and platelet count.

Biochemistry

Chemistry assessments will include uric acid, albumin, total protein, phosphate, calcium, sodium, potassium, chloride, bicarbonates, blood urea nitrogen (BUN), creatinine, fasting glucose, gamma GT, alkaline phosphatase (AP), aminotransferase AST and ALT, total bilirubin, total Cholesterol, HDL, LDL, triglycerides, CRP.

Serology

Serology assessments will include:

- Hepatitis B (HBs Ag),
- Hepatitis C (anti-HCV IgG, viral load only if positive antibody result),
- HIV (anti-HIV IgG, anti-HIV IgM),
- CMV (anti-CMV IgG* only even in case of positive result),
- HTLV-1 (anti-HTLV-1 IgG)

* In case of positive anti-CMV IgG result, no other dosages will be performed for confirming or not the infection. CMV infection will be assessed on investigator's judgment.

9.2.2. Urine analysis

Urinary test will be carried out at (V0) to screen for cannabinoid use.

Proteinuria, glycosuria using urine test strip will be tested at (V0).

A urinary pregnancy test dipstick will be used at (V0) and (V2) in female subjects.

9.3. Phenotypic assessment of the donors (baseline)

12mL of blood sample will be collected at inclusion visit (V1) and analyzed at local center for the assessment of the phenotypic of the donors to have a baseline for each donor:

Serology

4mL will be collected for serology assessments will include: Influenza.

Immunology assessments

8mL will be collected for immunology assessments that will include serum immunoglobulins (IgM, IgG, IgA, IgE).

Any laboratory parameters that the investigator judges to be clinically significant will be recorded as an adverse event. As such, clinically significant laboratory abnormalities will be followed until clinical resolution, improvement or stabilization (only relevant for standard lab repeated at V2).

9.4. Biological sample for evaluation of trial objectives

9.4.1. Blood samples

- Blood sample for genetic analysis (25mL)

Whole blood samples will be collected at V1 and V2 on heparin (20 mL) and EDTA (5 ml) and immediately shipped at temperature between 18°C and 25°C and within 6 hours to Institut Pasteur to the Center for Human Immunology (CIH) for storage before performing study analysis.

The following procedures will be performed from the sample (see appendix 18.1):

- 1) immunophenotyping of fresh whole blood samples by flow cytometry
- 2) Determination of the genetic architecture of the population-based study achieved using whole genome sequencing and SNPs haplotyping. (using DNA isolated from PBMCs/PMN cells)
- 3) EBV induced cell lines

EBV lymphoblastic cell lines will be generated by EBV transformation of B-Lymphocytes from the peripheral blood lymphocytes populations.

-
- Blood sample for TruCulture® - immune assays (50mL)

Blood samples will be used to measure cytokine/chemokine stimulated by 40 pattern-recognition receptors agonists (PRR agonists) or immune stimulators.

In vitro/ex vivo analyses on whole blood assays will be performed at V1 and V2 and are described in details in appendix 18.1.

All immune stimulations will be performed using whole blood TruCulture® medical devices. TruCulture® tubes, filled with the different stimulants will be provided in prepacked sets.

About 50mL of blood will be collected from the antecubital fossa (elbow pit) using regular pre-heparinized syringes. Syringes will be transferred to the laboratory where the blood filling into the TruCulture® tubes will be performed.

Specific work instructions for collection, incubation and handling will be provided within a TruCulture® handling manual.

The material is cryopreserved in dry ice (-80°C) at local center and will be shipped about once a week to Institut Pasteur to the Center for Human Immunology for storage before performing study analysis.

9.4.2. Stools and nasal swab samples

The stools sample and nasal swabs will be collected at V1 and V2 for characterizing the **evaluation of the metagenomic architecture of the population based on sequence analysis of bacterial, fungal and viral populations in fecal and nasal samples** (human Microbiome Phenotype).

➤ Stools sample

A collection device and a plastic bag for the transport labeled with the subject's identification number will be supplied to the subjects at V0 and V1. Subjects will produce and collect the faecal specimen at their home within 24 hours before their visits (V1, V2) and up to 2 days after the visits, using the collection device. The collection device containing the sample should remain in the subject's fridge until subject's visit to the unit.

Upon reception at the clinical site, the specimen container is cryopreserved in a freezer (-80°C) and will be shipped about once a week to Institut Pasteur to the Center for Human Immunology for storage before performing study analysis.

➤ Nasal swab

Specimens will be obtained with sterile, dry swabs, which are rotated five times around the inside of each nostril while applying constant pressure. Right and left nostril will be sampled separately. All swabs will be frozen (-80°C) upon collection from healthy individuals (Frank et al., 2010 PLOS One 5, e10598)⁽²⁾ at local site.

The material is frozen at -80°C at local center following and will be shipped about once a week to Institut Pasteur to the Center for Human Immunology for storage before performing study analysis.

➤ Stools and nasal swab analysis

The analysis are described in Appendix 18.1

9.4.3. Skin punch biopsy

The skin punch biopsy will be performed at V1 to **establish cell bank of genetically annotated fibroblasts cell lines and iPS cell lines.**

➤ Skin punch biopsies at V1

Skin punch biopsies will be performed at V1 under local anesthesia with appropriate disinfection of the skin with antiseptics, by a qualified physician. The biopsy will be taken using a sterile single use biopsy punch. The standard depth of the punch blade is 7mm. The biopsy is a standard 3mm round dermal punch, taken from the inner site of the upper arm. The skin biopsy is usually performed in less than 5 minutes.

Hemostasis will be achieved by pressure with a gauze pad.

Specific work and handling instructions for collection of the punch biopsy of the skin tissue will be provided within a biopsy handling manual. More details are given in appendix 18.2.

The subject will be recommended to clean the skin at biopsy site each day for reducing the infection risk.

The material collected will be shipped the same day of the collection at 4°C to the subcontractor Genethon (Evry, Ile de France, France) and before 3:00 PM.

The skin biopsies will be used to create an annotated collection of human fibroblast cell lines and potentially generate induced pluripotent stem cells (iPS cell lines) from fibroblasts, in turn permitting establishment of a wide variety of cellular populations for experimental study.

The iPS bank will be performed by Ectycell then it will be sent to Institut Pasteur to the Center for Human Immunology for performing study genetic analysis. The remaining samples will be stored at Institut Pasteur in the same department.

9.5. Sample storage

After the study, if the subject agrees their biological samples may be stored until their complete use for further research related to immune responsiveness.

If the subject agrees, the stored biological may be used for additional genetic analysis.

The collection will be stored at Institut Pasteur at the Center for Human Immunology (CIH).

10. RESULTS COMMUNICATION TO SUBJECTS

Upon completion of the study, the global results of the research will be communicated to the investigators. According to the French regulation, the subject may ask the investigator for the results or can consult the dedicated website.

Concerning the individual data, clinical examination findings including ECG, standard laboratory tests (biochemistry, haematology, hemostasis, serologies, immunology and urinary analysis including dipstick) will be communicated to the subjects. If these results are clinically significant or relevant the subject will be sent to a physician or to an appropriate unit for medical care. After the visits are completed, if clinically significant abnormal laboratory results are found, which could indicate a health hazard, the subject will be contacted in order to inform him/her so that he/she will be taken care of in appropriate manners.

The global results of the research will be available for volunteers through a website dedicated to the research.

11. SECURITY AND SAFETY EVALUATION

11.1. Definitions

Adverse Events (AE)

Any untoward medical occurrence in a clinical research subject and which does not necessarily have a causal relationship with this research.

Adverse Reaction (AR)

Any untoward medical occurrence in a clinical research subject and which has a causal relationship with this research.

Serious Adverse Event (SAE)

A serious adverse event is any untoward medical occurrence that:

- Results in death,
- Is life threatening (subject at risk of death at the time of the event),
- Requires inpatient hospitalization or prolongation of existing hospitalization,
- Results in persistence or significant disability/incapacity, or
- Is a congenital anomaly/birth defect
- Medical and scientific judgment should be exercised in deciding whether expedited reporting is appropriate in other situations, such as important medical events that may not be immediately life-threatening or result in death or hospitalisation but may jeopardise the subject or may require intervention to prevent one of the other outcomes listed in the definition above. These should also usually be considered serious (ICH E2A).

11.2. Expected Adverse events

The only unwanted effects expected during the participation of the subjects are:

- Those related to the blood collection (discomfort at puncture site, transient hematoma, more rarely faintness or syncope)
- Those related to the skin biopsy (Allergic reaction due to the local anesthesia, local infection, bleeding, scar risk, vagal faintness)
- Those related to the nasal swab (low bleeding, irritation)

11.3. Reporting of the Adverse Events

Any Adverse events occurring during the study will be reported in the CRF appropriate sections. For each adverse event, relevant information should be reported in the CRF including the nature, the timing of event occurrence and resolution, the severity, the outcome, the relationship to the research, the measures taken for the subject.

The severity of the event will be evaluated by the following scale:

- Mild: does not interfere with the usual subject activities
- Moderate: partially prevents the subject to perform his/her usual activities
- Severe: prevents totally the subject to perform his/her usual activities

The investigator should follow each adverse event until the event has resolved to baseline grade or better, the event is assessed as stable by the investigator, the subject is lost to follow up, or the subject withdraws consent. Every effort should be made to follow all serious adverse events considered to be related to study drug or trial-related procedures until a final outcome can be reported.

11.4. Notification of Serious Adverse Events to the sponsor

11.4.1. Investigator responsibilities

Any Serious adverse events (SAE) related to the research will be immediately (within 24h) reported to the selected CRO Clinical Service' Pharmacovigilance department by telephone or fax.

- [contact]
- [contact]

The relationship to the research will be first evaluated by the investigator then by the sponsor.

A written confirmation and a complementary detailed report will be sent to the select CRO.

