11.4.2. Sponsor responsibilities

Once the sponsor is informed of the SAE it must assess the relationship between the serious adverse event and the research.

The sponsor assesses if the SAE is expected or unexpected and the CRO Clinical Service' Pharmacovigilance department proceeds to the regulatory reporting, in particular to the Afsaps and to the CPP, and informs the investigators.

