12. DATA MANAGEMENT AND STATISTICAL METHODS

12.1. Data Management

A database located at Institut Pasteur (CIH) will be created under the responsibility of [name] to record all the study data (data base from Biotrial 's site and data base from Nutrinet-santé).

An electronic CRF (e-CRF) will be used to capture the study data on each investigational site. Any queries generated during the data management process will be tracked by the contracted data management CRO. It will be the study monitor's responsibility to ensure that all queries are resolved by the relevant parties. At the end of the study, the data base will be sent to Institut Pasteur in a way totally securised.

The nutrition data collected from the Nutrinet-Sante Study will be sent directly to Institut Pasteur at CIH. The data will be sent under pseudo-anonymised code (enrolment number) in a way totally secured. The Nutrinet's data that will be transferred will respect the MR001 (see 14.6.2).

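### Section 11.4.1 requires 24-hour notification only of SAEs that the investigator considers research-related, so an SAE called unrelated prompts no timely causality review by the sponsor

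*Protocol*

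**What the plan says.** Section 11.1 defines seriousness without reference to cause: "A serious adverse event is any untoward medical occurrence that" meets one of the listed criteria. Causally related events have their own term, Adverse Reaction: "Any untoward medical occurrence in a clinical research subject and which has a causal relationship with this research".

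Section 11.3 covers recording: "Any Adverse events occurring during the study will be reported in the CRF appropriate sections". The relationship to the research is among the items to be entered for each event.

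Section 11.4 covers notification to the sponsor, and its title refers to serious adverse events without restriction. Section 11.4.1 sets the duty: "Any Serious adverse events (SAE) related to the research will be immediately (within 24h) reported". The report goes to the pharmacovigilance department of the contracted research organisation. The section then says: "The relationship to the research will be first evaluated by the investigator then by the sponsor".

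Section 11.4.2 continues: "Once the sponsor is informed of the SAE it must assess the relationship between the serious adverse event and the research". The sponsor also judges expectedness, and the research organisation's pharmacovigilance department proceeds to regulatory reporting.

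Section 12.1 states when the study data reach the sponsor: "At the end of the study, the data base will be sent to Institut Pasteur in a way totally securised".

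**The concern.** A second causality assessment is useful mainly because it may differ from the first in either direction. Here the first assessment decides whether the second one is prompted at all. If the investigator attributes a serious event to another cause, 11.4.1 does not require notification, so the sponsor's step in 11.4.2 does not start. Expectedness and regulatory reporting follow from the same step and inherit the same condition.

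The study takes about 1,200 healthy volunteers at V0, 1,000 at V1 and up to 500 for a skin biopsy, with no investigational product. Harm from study procedures is therefore the main safety question. At stake is timely oversight of a serious event whose link to a procedure was missed at the site.

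**Working it through.** No arithmetic reproduces a figure here, because the protocol states none on this point. The check is to read the sections side by side and follow an SAE through them.

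**1. Is the condition a real restriction?** Yes. Section 11.1 defines an SAE by seriousness alone and names causally related events separately. Where the protocol means every event in the study, as in 11.3, it says so. The events described in 11.4.1 are therefore a subset of SAEs.

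**2. Who applies it?** Section 11.4.1 is headed as the investigator's responsibilities, and the investigator's causality evaluation comes first. The sponsor cannot apply the condition to an event it has not yet been told about.

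**3. The two branches.**
- *Investigator says related:* the SAE is reported within 24 hours, the sponsor is informed and reassesses causality, expectedness is judged and regulatory reporting follows. The sponsor may agree or downgrade.
- *Investigator says unrelated:* the SAE is entered in the CRF under 11.3. Section 11.4 requires no notification, so the event that starts the sponsor's assessment in 11.4.2 does not occur.

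**4. Is there another timed route?**
- Section 11.3: CRF entry of all events, with no deadline for informing the sponsor and no sponsor causality review.
- Section 7.2: withdrawals due to an AE or SAE are referred back to section 11, which adds no route. The primary reason for withdrawal goes on the end-of-study form.
- Sections 13.1.1, 13.1.2 and 13.2: access to source documents, regular monitoring visits and possible audits. None names an SAE task or a time limit.
- Section 12.1: database transfer at the end of the study.

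**5. How long could the delay be?** Assume that the end of the study means the last subject's last visit and that monitoring does not pick up the event. An SAE near the first enrolment could then wait almost the whole conduct period. That period is about 1 year in section 3.1 and 14 months in section 3.2.3, against 24 hours for an event called related. Earlier discovery at a monitoring visit is possible but is not required.

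**The case against.** Several objections have force.

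*The sponsor is not blind to these events.* A reader might infer that the sponsor never sees an SAE called unrelated. The documents do not support that: every event is in the CRF with its causality call, sponsor-assigned monitors visit regularly with access to source documents, and the sponsor receives the database. What is missing is notification, and with it a prompt to reassess in time.

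*No final count is biased by construction.* A reader might also infer that the reported number of research-related SAEs must come out too low. That does not follow. Nothing bars the sponsor from reclassifying an event found in the database, and nothing says that a final count uses only notified cases. The protocol also states no safety objective or outcome, so no planned estimate is affected. The gap is one of timing and of what triggers review.

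*A review limited to suspected-related SAEs can be coherent.* The sponsor's step still does work, since it rechecks causality and judges expectedness. This is fair: the text can be followed literally without a strict contradiction. It nevertheless leaves the second relatedness assessment working in one direction only, which sits badly with a two-step evaluation and with the unrestricted title of 11.4.

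*It may be loose drafting.* Possibly, but the separate Adverse Reaction term favours the restrictive reading, and a site would be entitled to follow it.

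*The likely harms are ones the investigator will recognise.* Section 11.2 lists syncope, local infection and bleeding among the expected effects, so the investigator is primed to call them related. This lowers the probable number of missed cases but does not supply the missing route.

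**Conclusion.** The point holds as a defect in the notification rule. As written, an SAE that the investigator considers unrelated is recorded but not notified, so neither a timely sponsor reassessment nor a regulatory evaluation is prompted. Through the notification route, causality can be confirmed or downgraded but not upgraded.

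The size cannot be given as a number of events. The protocol states no expected SAE rate and no figure for how often an investigator misjudges causality, and any chosen value would be invented. That the absolute number is small is an assumption. It rests on the absence of an investigational product, on the procedures used (blood draws, swabs and, for some subjects, a 3 mm punch biopsy) and on participation of at most about 8 weeks.

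The conclusion rests on reading the relatedness condition in 11.4.1 as 11.1 defines its terms, and on no other section of the protocol setting a timed route. It is worth correcting because it concerns safety oversight of healthy volunteers and the remedy is very small. Sample size, precision and planned analyses are unaffected.

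**What to change.** In section 11.4.1, delete the four words that limit the duty to research-related events, so that every SAE is notified within 24 hours whatever the investigator's opinion on causality. The investigator's opinion is still recorded and sent with the report. The two-step assessment in 11.4.1 and 11.4.2 then works in both directions, and the text agrees with the title of 11.4.

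When making the change, note that section 11.3 also uses relatedness in its sentence on following SAEs to a final outcome. That sentence concerns follow-up, not notification, and this edit leaves it as it stands.

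The cost is the wording change through the usual amendment route, a note to the single site and a few additional SAE forms. No change to the CRF content, sample size or analysis is needed.

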11.4.2. Sponsor responsibilities

Once the sponsor is informed of the SAE it must assess the relationship between the serious adverse event and the research.

The sponsor assesses if the SAE is expected or unexpected and the CRO Clinical Service' Pharmacovigilance department proceeds to the regulatory reporting, in particular to the Afsaps and to the CPP, and informs the investigators.

12. DATA MANAGEMENT AND STATISTICAL METHODS

12.1. Data Management

A database located at Institut Pasteur (CIH) will be created under the responsibility of [name] to record all the study data (data base from Biotrial 's site and data base from Nutrinet-santé).

An electronic CRF (e-CRF) will be used to capture the study data on each investigational site. Any queries generated during the data management process will be tracked by the contracted data management CRO. It will be the study monitor's responsibility to ensure that all queries are resolved by the relevant parties. At the end of the study, the data base will be sent to Institut Pasteur in a way totally securised.

The nutrition data collected from the Nutrinet-Sante Study will be sent directly to Institut Pasteur at CIH. The data will be sent under pseudo-anonymised code (enrolment number) in a way totally secured. The Nutrinet's data that will be transferred will respect the MR001 (see 14.6.2).

12.2. Sample size and power

It is considered that the sample planned for this study (a total of 1000 healthy donors with 100 in each gender x age strata combination) will be large enough to ensure sufficient statistical power to the planned analyses, based on the considerations described below:

- The power of association testing depends on several criteria: sample size, marker density and the QTL genetic effect on expression levels (Zondervan)⁽¹²⁾. Our sample size, particularly when it comes to eQTL analyses, are significantly larger than those recently used to successfully detect steady state eQTLs, based on 60 and 69 individuals of European and African-descent, respectively (Montgomery) (Pickrell)⁽⁷⁾⁽⁹⁾.
- In terms of precision of the estimations, the total sample size of 1000 donors will provide a precision (half the 95% CI coverage) of 0.062 standard deviations to estimations of means, and a precision of at least 0.03 to estimations of percentages. Focusing on each gender x age strata combination, the sample size of 100 in each cell will provide precisions of 0.20 standard deviations to estimates of means and 0.10 to estimates of percentages.

